19.2 INTERIM ANALYSES

When an obvious difference in recurrence rate or survival between the two treatment groups appears during the inclusion phase of the trial, it is considered unethical to continue accrual of patients.

Formal interim analyses will be carried out after each 20 recurrences and each 20 in-hospital mortalities. For this purpose, recurrences and in-hospital mortalities have to be reported to the coordinating center within 2 weeks after detection.

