3.4 STATISTICS & RANDOMIZATION

Using log rank statistics with a power of 80 % and a type I error of 5%, 1275 patients are needed to detect a difference between both treatment arms of 5% in locoregional recurrence rate 3 years postoperatively, assuming a 10% recurrence rate in the open group. Randomization will be 2:1, laparoscopic versus open resection respectively. Analyses will be on "intention to treat" basis. Randomization is stratified for each participating center, planned procedure, radiotherapy and sex.

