7 ETHICS

The trial must be approved by the appropriate ethics committee of each participating institution prior to its entry into the study. Eligible patients should be informed in person by the treating surgeon and receive written information about the trial in their own language. Informed consent should be obtained from each patient according to the guidelines of the local ethical committee, prior to randomization into the study. Patients remain free to withdraw at will at any time from the study without giving reasons.

To guarantee optimal treatment for patients in both treatment arms, interim analyses will be performed to compare survival and recurrence in both treatment arms. If differences of survival or recurrence rates are significant, accrual of patients will be stopped.

To assess the feasibility of laparoscopic rectal cancer resection, a phase II trial will precede the accrual of patients in this trial.

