19 STATISTICAL CONSIDERATIONS

19.1 SAMPLE SIZE AND STATISTICAL ANALYSIS

Locoregional cancer recurrence rate of operated patients with cancer stages <IV after 3 years is currently about 10 %. The primary objective of the study is to show that laparoscopic surgery does not lead to an increased locoregional recurrence rate. Equivalence of both treatments is considered to be shown if the resulting two-sided 95% confidence limits of the difference in 3-yrs locoregional recurrence rates excludes a difference greater than 5%. At a randomization ratio of 2:1, and assuming a recurrence rate of 10% in each group, 850 laparoscopic patients and 425 open patients are required to have a power of 80% for this study.

All analyses will be carried out on an "intention to treat" basis: patients, whose randomized laparoscopic operation was converted to an open resection, will be analyzed in the laparoscopic group.

Eight weeks operative mortality, pathological resection margins and complication rates will be compared using the Chi-square test. Locoregional recurrence rate, disease free survival and overall survival will be compared between the two procedures using log-rank statistic, adjusted for center. Exploratory analysis of the prognostic effects of various baseline data will be done using multivariate Cox-regression. Analysis of the primary endpoint will be performed 1.5 - 2 years after inclusion of all patients.

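### Sections 7 and 19.2 stop accrual on a significant or obvious difference at an unlimited series of interim looks with no boundary; at the 5% level about 11–13% of equal-arm trials would stop falsely

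*Protocol*

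**What the plan says.** Section 19.2 fixes the schedule: "Formal interim analyses will be carried out after each 20 recurrences and each 20 in-hospital mortalities". It gives no maximum number of looks. It also calls further accrual unethical once an obvious difference in recurrence or survival appears during the inclusion phase.

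Section 7 states the consequence as a rule: "If differences of survival or recurrence rates are significant, accrual of patients will be stopped". It gives no level for significance.

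The only error level in the protocol is in Section 3.4: "Using log rank statistics with a power of 80 % and a type I error of 5%, 1275 patients are needed". Section 19.1 bases the primary conclusion on a different rule: "Equivalence of both treatments is considered to be shown if the resulting two-sided 95% confidence limits of the difference" in 3-year locoregional recurrence excludes more than 5 points. That section names the log-rank test for comparing locoregional recurrence and survival.

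Section 19.2 does not say which recurrences count towards each block of 20. The general definition in Section 16.1 covers distant as well as locoregional disease.

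**The concern.** The protocol itself fixes the schedule, the trigger and the action. Someone applying Section 7 at a look has only the 5% level to work with. A 5% test repeated on accumulating data finds a false difference far more often than 5% of the time, and here each positive result stops accrual.

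The two trigger wordings also conflict. A result at p=0.04 is significant, but few would call it obvious, so the same data could stop accrual under Section 7 and not under Section 19.2. At stake is a chance halt of a trial that Section 4.4 justifies by the need for evidence before laparoscopic TME enters routine practice.

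**Working it through.** **1. The plan's own sample size.** Inputs from Section 19.1: 10% recurrence in each arm, 5-point margin, two-sided 95% limits, 80% power, 2:1 allocation.

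Open arm: n = (1.960 + 0.842)² × 0.10 × 0.90 × (1 + 1/2) / 0.05² = 7.849 × 54 ≈ 424. Total 3 × 424 = 1272, against 1275 stated.

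Power at 850 and 425: SE = √(0.09/850 + 0.09/425) = 0.01782, and Φ(0.05/0.01782 − 1.96) = Φ(0.845) = 80.1%.

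The figure reproduces as a non-inferiority size at 2.5% per side. Read as a two-sided 5% test for a difference, as Section 3.4 words it, the total would be 936 (10% v 5%) or 1578 (10% v 15%). The effect of the looks must therefore be worked out separately for a false difference and for false non-inferiority.

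**2. Number of looks.**
- Locoregional recurrences only: 0.10 × 1275 = 127.5, so six complete blocks of 20 over the whole 3-year follow-up.
- Any recurrence (assumed 30%): 0.30 × 1275 = 382.5, so about 18 to 19 blocks.
- Looks during accrual only, locoregional: on average 2.7 to 4.1 (step 5).

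**3. Chance of at least one false difference, recurrence series.** Assumption: two-sided 0.05 at every look. With equally spaced looks, Z_k = S_k/√k, where S_k is the sum of k independent standard normals. The quantity is P(|Z_k| > 1.96 at some look), from 400,000 simulations:

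| Looks | Chance |
|---|---|
| 1 | 5.0% |
| 2 | 8.3% |
| 3 | 10.7% |
| 4 | 12.5% |
| 6 | 15.4% |
| 6 plus a final test at 127.5 events | 16.1% |
| 18 | 23.9% |

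**4. Adding the mortality series.** The protocol gives no in-hospital mortality rate. Assuming 2–5%, there would be 25.5 to 63.75 deaths, hence one to three looks. Treating the two series as independent, the combined chance is 1 − (1 − a)(1 − b):
- four recurrence looks plus final, one mortality look: 1 − (1 − 0.148)(1 − 0.050) = 19%;
- six recurrence looks plus final, three mortality looks: 1 − (1 − 0.161)(1 − 0.107) = 25%.

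**5. Whole-trial simulation with looks during accrual only.** Assumptions: uniform accrual over 3, 5 or 6 years, constant hazard, no dropout, locoregional recurrences only, unadjusted log-rank at |Z| > 1.96, then the Section 19.1 confidence-limit rule at 3 years. There were 6,000 runs per case (simulation error about 0.4 point on the false-stop rate).

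| Accrual | Mean looks | False stop, equal arms | False stop or final log-rank positive | Completes accrual and shows non-inferiority | False non-inferiority at 15% v 10% |
|---|---|---|---|---|---|
| 3 years | 2.7 | 10.9% | 14.1% | 73.4% | 2.1% |
| 5 years | 3.8 | 12.5% | 14.9% | 72.5% | 2.1% |
| 6 years | 4.1 | 12.6% | 14.7% | 72.7% | 2.0% |
| No looks | – | – | – | 81.2% | 2.1% |

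**6. The same calculations with p<0.001 (|Z| > 3.29) at each interim look.** In the model of step 3 with a final two-sided 0.05 test, the overall error for the recurrence series is 5.1% with 2 to 6 interim looks and 5.3% with 18. Re-running step 5 with 3.29 in place of 1.96 gives false stops in 0.2–0.3% of equal-arm trials, and 81% complete accrual and show non-inferiority.

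**The case against.** The strongest reply is that the primary conclusion is protected. It rests on confidence limits excluding a 5-point excess, and stopping for a difference does not make that easier to achieve wrongly. This stands. A reader might infer that the error of the trial's main claim rises to 13–24%, but step 5 puts false non-inferiority at 2.0–2.1% with the looks and 2.1% without. What is inflated is the chance of falsely declaring a difference and stopping.

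Second, no single inflated figure follows from the documents. Every value above assumes 0.05 per look and a number of looks, and the word obvious in Section 19.2 could mean something stricter. This also stands, so the size is given as a range. It does not rescue the rule, because the protocol never says what stricter level applies.

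Third, a reader might infer that a trial stopped at 40 recurrences could not meet the 5-point criterion, since the half-width at that information is 1.96 × 0.01782 × √(127.5/40) = 6.2 points. The protocol does not support this. It stops accrual, not follow-up, and patients already enrolled go on to their 3-year imaging (Section 15.1). Under the accrual assumptions of step 5, about 997, 776 or 710 patients would be enrolled at 40 events. Their eventual half-width is 1.96 × √(0.405/n) = 3.9, 4.5 or 4.7 points, below 5 in each case. If the limits are applied to stopped trials after full follow-up, about 80% of all equal-arm trials still show non-inferiority. The drop to 73% therefore counts trials that both complete accrual and succeed.

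Fourth, boundaries are often left to a statistical analysis plan, which is not at hand, and the section on the monitoring committee is not in the public text. A plan could supply a boundary, but it would have to override a mandatory stop written into Section 7.

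**Conclusion.** The point holds in this form: Sections 7 and 19.2 prescribe an open-ended series of formal looks and a mandatory stop of accrual, under two different triggers and with no threshold or error control.

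Read at the stated 5% level, the chance of a false difference in the recurrence series is about 8% (two looks) to 24% (about 18 looks, if any recurrence counts and about 30% of patients recur). On the narrowest reading, with locoregional recurrences and looks during accrual only, it is about 11–13% false stops, or 14–15% including the final log-rank test. Mortality looks add to this.

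The non-inferiority error under Section 19.1 is not inflated. The cost falls on delivery: the share of equal-arm trials that complete accrual and show non-inferiority drops from about 81% to about 73%, below the 80% power the plan states. These sizes rest on the assumed level per look, accrual time, constant hazard and event rates given above. The absence of a boundary does not depend on them.

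**What to change.** In Sections 7 and 19.2:
- use one trigger wording in both places;
- state which recurrences are counted towards each block of 20. Limiting them to locoregional recurrence is one option, not a required correction, because Section 7 monitors recurrence and survival more broadly;
- replace the bare reference to significance with a group-sequential boundary for each monitored series, for example Haybittle-Peto (two-sided p<0.001 at each interim look) or O'Brien-Fleming-type alpha spending;
- keep the final two-sided 95% confidence-limit rule of Section 19.1.

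This is a few sentences, does not change the sample size, and should be in place before the first look.

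The downside is that early stopping for a moderate true difference becomes less likely. In the step 5 simulation at 15% v 10%, accrual stops early in about 45–64% of trials at 0.05 per look and about 4–12% at p<0.001. Detection by the end of the trial changes little, from about 75–78% to about 72%. A sponsor wanting more chance of a late-accrual stop could choose the spending approach.

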20 ORGANIZATION

20.1 PROTOCOL AND WRITING COMMITTEE

The protocol committee is responsible for organization of the trial. The writing committee will be responsible for publication and presentation of all data. Publications will be coordinated by the Erasmus Medical Center.

20.2 DATA MONITORING

A trial monitor will be appointed to monitor trial progress on site, as frequently as seen fit. During these visits, case record forms and related records will be checked for completeness and consistency.

20.3 QUALITY CONTROL

To ensure quality control, a TME can only be performed if one member of the operating team has experience with at least 5 procedures. To assess the feasibility of laparoscopic rectal cancer resection, a phase II trial will precede the accrual of patients in this trial.

An instructional video on the laparoscopic TME technique will be distributed. If experience is lacking, special training sessions to individual surgeons on the technique of TME and autonomic nerve sparing will be organized during on-site instructional operations by experienced surgeons in the field. Surgeons with expertise in the TME procedure should initially assist surgeons with extensive laparoscopic experience to train and standardize the laparoscopic procedure.

Specimen examination by pathologists will be according to rules described in the protocol.

20.4 PRESENTATION & PUBLICATION

All presentations or publications will be in the name of the 'COLOR II Study Group'. Local accrual rates of each participating hospital will be listed in every publication or presentation. The sponsor has no influence over implementation of the research and content of the publications.

Data assessed nationally, on quality of life, costs and validation of endosonography can be published or presented by smaller groups of authors without international consent. Publication or presentation of these data can only be possible when it becomes clear that patients were included in COLOR II. If a center violates these rules, exclusion from COLOR II and exclusion from authorship will be the consequence. Publication of data will not take place until accrual of patients has been stopped.

21.3 APPENDIX III: TNM CLASSIFICATION OF COLORECTAL CANCER

- T: Primary tumor
- Tx Primary tumor cannot be assessed
 - T0 No evidence of primary tumor
 - Tis Carcinoma in situ: intraepithelial or invasion or invasion of lamina propria
 - T1 Tumor invades submucosa
 - T2 Tumor invades muscularis propria
 - T3 Tumor invades through muscularis propria into subserosa or into non peritonealized pericolic or perirectal tissue
 - T4 Tumor directly invades other organs or structures and/or perforates visceral peritoneum
- N: Regional Lymph Nodes
- Nx Regional lymph nodes cannot be assessed
 - N0 No regional lymph metastases
 - N1 Metastases in 1-3 pericolic or perirectal lymph nodes
 - N2 Metastases in 4 or more pericolic or perirectal lymph nodes
- M: Distant metastasis
- Mx Metastasis cannot be assessed
 - M0 No distant metastasis
 - M1 Distant metastasis present

21.4 APPENDIX IV: STAGE GROUPING

Stage	Primary Tumor	Regional lymph nodes	Distant metastases	Dukes' stage
0	Tis	NO	M0	
I	T1	NO	M0	A
	T2	NO	M0	
II	T3	NO	M0	B
	T4	NO	M0	
III	Any T	N1	M0	C
	Any T	N2/	M0	
IV	Any T	Any N	M1	D

21.5 APPENDIX V: INVESTIGATOR SITE FILE

The investigator site file is made for each participating center. In this file all forms, lists and data concerning the COLOR II trial are stored. The contents of this file are listed below.

1. Registration form not included / excluded patients
All patients suspected of having a malignant rectal tumor, who do not meet the inclusion criteria or are excluded postoperatively, should be registered in this form.
2. Decoding list of patients
List of patients with randomization numbers and their corresponding hospital patient identification numbers. As only randomization numbers should be mentioned in the case record forms, this list is used to find patient files from trial patients if needed.
3. Decoding list of surgeons COLOR II trial
List of surgeons who operate on trial patients with their corresponding codes. Names of surgeons should not be mentioned in the case record forms.
4. Signed informed consent forms.
Copies cannot be sent to the coordinating center, because of privacy reasons.
5. Ethical committee approval & correspondence
6. Protocol & amendments
7. Copies of completed case record forms and follow up forms
Original completed forms should be sent to the coordinating center.
8. Monitor log & reports

[figure not shown]
21.6 APPENDIX VI: QUALITY OF LIFE SCHEDULE

QUESTIONNAIRE	PREOP	POSTOP				
	1 day	1 day	Week 4	Month 6	Month 12	Month 24
Euroqol-5D	X		X	X	X	X
EORTC QLQ-C30	X		X	X	X	X
EORTC QLQ-CR38	X		X	X	X	X
EORTC QLQ-PR25*	X		X	X	X	X

Table 1. Current questionnaires

* Only the first subset of questions (questions 31 to 37)

21.7 APPENDIX VI: FLOW CHART OF RECTAL CANCER PATIENTS

21.8 APPENDIX VII: CASE RECORD FORMS

See next pages

COLOR II

Dept. of Surgery, QEII Health Sciences Centre
[name]
[name], Halifax, Nova Scotia
Canada [name]
[contact]
[contact]

Date:**Procedure:** LAP / OPEN**Rand nr:****Doctor:**

IDENTIFICATION (no 1 - 6)**If appropriate, please encircle correct figure, more than one can be encircled per question**

1. hospital :
2. randomization no. :
3. date of birth (dd/mm/yyyy) :
4. gender : 1 male
2 female
5. date of randomization (dd/mm/yyyy) :
6. randomized procedure : 1 laparoscopic
2 open
- 6A. clinical TNM stage: T _____ N _____ M _____

COLOR II

Dept. of Surgery, QEII Health Sciences Centre
[name]
[name], Halifax, Nova Scotia
Canada [name]
[contact]
[contact]

Date:

Procedure: LAP / OPEN

Rand nr:

Doctor:

PREOPERATIVE PERIOD < 28 days prior to surgery (no 7 - 17)

If appropriate, please encircle correct figure, more than one can be encircled per question

7. date of admission (dd/mm/yyyy):

8. ASA class :

9. length : cm

10. weight : kg

11. no. of previous abd. operations :

12. date of diagnosis (dd/mm/yyyy) :

13. exact location of tumor : cm (distal border from anal verge)

- determined by : 1 rectoscopy
- 2 colonoscopy
- 3 MRI
- 4 CT

14. proposed type of resection :

- 1 Resection without TME (= Partial Mesorectal Excision)
- 2 Resection with TME with preservation of the anus
- 3 Resection with TME without preservation of the anus (APR)

15. previous radiotherapy of the pelvis : 0 no
1 yes

16. preoperative radiotherapy : 0 no
(if yes, please specify dose and duration) 1 yes X Gy

16a. preoperative chemotherapy : 0 no
(if yes, please specify dose and duration) 1 yes

16b. Participation in Quality of Life substudy : 0 no
1 yes

COLOR II

Dept. of Surgery, QEII Health Sciences Centre
 [name]
 [name], Halifax, Nova Scotia
 Canada [name]
 [contact]
 [contact]

Date:**Procedure:** LAP / OPEN**Rand nr:****Doctor:****INTRAOPERATIVE PERIOD** (no 18 - 39)

If appropriate, please encircle correct figure, more than one can be encircled per question

18. name(s) of surgeon(s) :
- 18a. experience (last year) : < 10 lap colorectal procedures
 10 - 20 lap colorectal procedures
 > 20 lap colorectal procedures
19. date of surgery (dd/mm/yyyy) :
20. performed operative procedure : 1 resection without TME (= Partial ME)
 2 resection with TME and preservation of the anus
 3 resection with TME without preservation of the anus (APR)
21. please specify level of distal transaction : cm
(distance between distal transaction & dentate line)
22. ureter stent : 0 no
 1 yes
23. presence of fibrosis considered to be due to radiation : 0 no
 1 yes
24. macroscopic metastases : 0 no
 1 liver
 2 peritoneal
 3 mesentery
 4 other :
25. macr. invasion adj. organs : 0 no
(if yes, please mention which organ) 1 yes please specify:
26. Degree of pelvic autonomic nerve preservation:
 1. Total preservation of autonomic nervous system. (hypogastric and pelvic preservation procedure)
 2. Bilateral preservation of parasympathetic nerve system with complete removal of the sympathetic system. (bilateral pelvic preservation procedure)
 3. Unilateral preservation of parasympathetic nerve system with complete removal of the sympathetic system. (unilateral pelvic preservation procedure)

COLOR II

Dept. of Surgery, QEII Health Sciences Centre
 [name]
 [name], Halifax, Nova Scotia
 Canada [name]
 [contact]
 [contact]

Date:**Procedure:** LAP / OPEN**Rand nr:****Doctor:**

27. if appropriate, reason for incomplete preservation:

1. tumor invasion
2. other :

28. length of incision : cm

29. location of incision : 0 none
 1 transverse right
 2 transverse left
 3 Pfannenstiehl
 4 other:

30. anastomosis : 0 no (stoma)
 1 handsewn
 2 circular stapler; size : mm
 3 other:

31. anastomosis configuration :

- | | | | | |
|---|--------------|--------------------------|-----------|--------------------------|
| 0 | no (stoma) | | | |
| 1 | end to end |  | ileostomy |  |
| 2 | end to side |  | ileostomy |  |
| 3 | side to side |  | ileostomy |  |
| 4 | side to end |  | ileostomy |  |
-
- | | | | | | |
|--|--|--------------------------|---------|--------------------------|----------------------|
| | |  | J-pouch |  | transverse colostomy |
| | |  | J-pouch |  | transverse colostomy |

31a. Type of stapler used to transect the rectum

- | | | | | | | |
|---|----------------|--------------------------|------|--------------------------|-------|---------------|
| 1 | Roticulator |  | blue |  | green | firings |
| 2 | Curvature |  | blue |  | green | firings |
| 3 | Linear stapler |  | blue |  | green | firings |
| 4 | Other |  | blue |  | green | firings |

32. blood loss : ml

33. skin to skin time : minutes

COLOR II

Dept. of Surgery, QEII Health Sciences Centre
 [name]
 [name], Halifax, Nova Scotia
 Canada [name]
 [contact]
 [contact]

Date:**Procedure:** LAP / OPEN**Rand nr:****Doctor:**

34. complication(s) : 0 none
 1 bleeding
 2 fixation of the tumor
 3 gastrointestinal perforation
 4 adhesions
 5 hypercapnia
 6 anastomosis related problems
 7 injury to ureter
 8 nerve injury
 9 perforation tumor
 10 other:

35. wound protection : 0 no
 (if yes, please mention kind of) 1 yes please specify:

PLEASE FILL OUT NEXT QUESTIONS IN CASE OF A LAPAROSCOPIC PROCEDURE

36. laparoscopic operative steps : 1 inspection
 2 mobilization of bowel
 3 ligation of main vessels
 4 oral transection of bowel
 5 aboral transection of bowel
 6 resection of bowel
 7 anastomosis

38. conversion : 0 no
 1 yes

39. if appropriate, reason for conversion :

COLOR II

Dept. of Surgery, QEII Health Sciences Centre
[name]
[name], Halifax, Nova Scotia
Canada [name]
[contact]
[contact]

Date:**Procedure:** LAP / OPEN**Rand nr:****Doctor:**

POSTOPERATIVE PERIOD 1-28 days after surgery; day of operation = day 0 (no 40 - 47)**If appropriate, please encircle correct figure, more than one can be encircled per question**

40. date of fluid intake > 1000 ml : (dd-mm-yyyy)

41. date of first passage of stool : (dd-mm-yyyy)

42. date of discharge from hospital : (dd-mm-yyyy)

43. if appropriate, date and nature of complication(s)

date (dd-mm-yyyy):

- 1 anastomotic leakage
- 2 cardiac complications:
- 3 respiratory complications:
- 4 abscess
- 5 ileus
- 6 other:

44. if appropriate, date and nature of re-intervention(s):

date (dd-mm-yyyy):

nature:

45. if appropriate, date and cause of death:

date (dd-mm-yyyy):

cause:

46. if appropriate, date, cause and duration of readmission:

date (dd-mm-yyyy):

cause:

readmission:

COLOR II

Dept. of Surgery, QEII Health Sciences Centre
[name]
[name], Halifax, Nova Scotia
Canada [name]
[contact]
[contact]

Date:**Procedure:** LAP / OPEN**Rand nr:****Doctor:**

47. pain medication during first 3 days

Please mention what kind of medication, quantity (mg) and, where appropriate, speed of pump (mg/ml per hour)

Postoperative day 1

1 opiates :

2 non-opiates :

3 epidural :

Postoperative day 2

1 opiates :

2 non-opiates :

3 epidural :

Postoperative day 3

1 opiates :

2 non-opiates :

3 epidural :

COLOR II

Dept. of Surgery, QEII Health Sciences Centre
[name]
[name], Halifax, Nova Scotia
Canada [name]
[contact]
[contact]

Date:**Procedure:** LAP / OPEN**Rand nr:****Doctor:**

Please add this information form for the pathologist to the resected specimen

COLOR II TRIAL

A randomized clinical trial comparing laparoscopic and open surgery for rectal cancer

Dear colleague,

The COLOR II trial is a randomized clinical trial comparing laparoscopic and open surgery for rectal cancer. The primary endpoint is locoregional recurrence three years post-operatively. In order to assess relevant oncological parameters, the pathological examination of the specimen is of utmost importance. Below you'll find the items which will be recorded for the COLOR II trial. You are kindly asked to document these items in your examination report.

Please provide the following data on pathology

- Completeness of resection

Complete	Intact mesorectum with only minor irregularities of the mesorectal surface up to the dissection level. No defect is deeper than 5 mm. No coning towards the distal margin of the specimen. Smooth circumferential resection margin.
Nearly Complete	Moderate bulk to the mesorectum, no visible muscularis propria, moderate coning, irregular circumferential resection margin.
Incomplete	Little bulk to the mesorectum with defects down onto muscularis propria and/or very irregular circumferential resection margin, coning.

- Size of tumor
- Distance of tumor from circumferential resection margin
- Distance of tumor from proximal resection margin
- Distance of tumor from distal resection margin
- If appropriate, position of tumor with respect to peritoneal deflection
- Type and differentiation of tumor
- Tumor tissue in surgical margins (i.e. radicality)
- Number of lymph nodes harvested
- Number of lymph nodes in proximal part of mesentery, that means all lymph nodes not along resected bowel (if none, please mention)
- If appropriate, nature of metastases
- If appropriate, synchronous colorectal pathology
- pTNM classification

COLOR II

Dept. of Surgery, QEII Health Sciences Centre
 [name]
 [name], Halifax, Nova Scotia
 Canada [name]
 [contact]
 [contact]

Date:**Procedure:** LAP / OPEN**Rand nr:****Doctor:****PATHOLOGY** (no 48 - 60)

If appropriate, please encircle correct figure, more than one can be encircled per question

48. completeness of resection

1. complete = intact mesorectum with only minor irregularities of the mesorectal surface up to the dissection level. No defect is deeper than 5 mm. No coning towards the distal margin of the specimen. Smooth circumferential resection margin on slicing.
2. nearly complete = the majority of the mesorectum has been removed, no visible muscularis propria, moderate coning, irregular circumferential resection margin.
3. incomplete = mesorectum with defects down onto muscularis propria and/or very irregular circumferential resection margin, coning.

49. size of tumor : x cm

50. distance from circumferential resection margin : cm

51. distance from proximal resection margin : cm

52. distance from distal resection margin : cm

~~53. position of tumor with respect to peritoneal deflection : cm~~

54. type and differentiation of tumor :

55. tumor tissue in surgical margins : 0 no
 1 oral
 2 aboral
 3 circumferential
 4 other :

56. no. of lymph nodes harvested :

57. no. of lymph nodes in proximal part of mesentery :

*(all lymph nodes **not** along resected bowel)*

58. if appropriate, nature of metastases :

59. if appropriate, nature of synchronous colorectal pathology:

60. pTNM classification : pT N M

COLOR II

Dept. of Surgery, QEII Health Sciences Centre
[name]
[name], Halifax, Nova Scotia
Canada [name]
[contact]
[contact]

Date:

Procedure: **LAP / OPEN**

Rand nr:

Doctor:

FOLLOW UP FORM FOR VISIT 1-7 YEAR(S) AFTER SURGERY

If appropriate, please encircle correct figure, more than one can be encircled per question

- 61. date of visit (dd/mm/yyyy) :
- 61A. Clinical TNM stage : T _____ N _____ M _____
- 62. recurrence : 0 no
(if yes, please fill out recurrence form) 1 yes
- 63. complications : 0 no
1 incisional hernia, please specify location
(which port or incision)
.....
2 complaints of bowel function, other than ileus
3 stress urinary incontinence
4 sexual dysfunction
5 fecal incontinence
6 other :
- 63a. Bowel obstruction : 0 no
1 yes operative
 conservative
- Cause of bowel obstructions : 1 benign
2 malignant
3 unknown
- 64. postoperative adjuvant therapy : 0 no
1 yes
- 65. re-admissions : 0 no
(if yes, please fill out event form) 1 yes
- 66. re-interventions : 0 no
(if yes please fill out event form) 1 yes

COLOR II

Dept. of Surgery, QEII Health Sciences Centre
[name]
[name], Halifax, Nova Scotia
Canada [name]
[contact]
[contact]

Date:**Procedure:** LAP / OPEN**Rand nr:****Doctor:**

RECURRENCE FORM

If appropriate, please encircle correct figure, more than one can be encircled per question

107. date of diagnosis of (re)recurrence (dd-mm-yyyy) :
108. number of recurrence (first, second, etc.) :
109. nature of recurrence : 1 locoregional
2 liver metastasis
3 lung metastasis
4 trocar wound recurrence
5 minilaparotomy wound recurrence
6 laparotomy wound recurrence
7 other :
110. date of cancer related death (dd-mm-yyyy) :

**When completed, please fax this form to the coordinating center:
Dalhousie University, Halifax, Canada**

[contact]

COLOR II

Dept. of Surgery, QEII Health Sciences Centre
[name]
[name], Halifax, Nova Scotia
Canada [name]
[contact]
[contact]

Date:**Procedure:** LAP / OPEN**Rand nr:****Doctor:**

RECURRENCE FOLLOW UP FORM**In case of re-recurrence, please fill out a new recurrence form**111. treatment : *(if appropriate, please describe type of procedure)*

0 no

1 curative resection :

2 palliative resection :

3 other :

112. date of cancer related death (dd/mm/yyyy) :

**When completed, please fax this form to the coordinating center:
Dalhousie University, Halifax, Canada**

[contact]

COLOR II

Dept. of Surgery, QEII Health Sciences Centre
[name]
[name], Halifax, Nova Scotia
Canada [name]
[contact]
[contact]

Date:**Procedure:** LAP / OPEN**Rand nr:****Doctor:**

FORM FOR EVENTS**Please don't forget to mention randomization number in upper right corner**

113. Date of event (dd-mm-yyyy) :
114. Sort event :
115. Date of death (dd-mm-yyyy) :
116. Cause of death :
117. Cause of bowel obstruction : 0 no bowel obstruction
1 herniation
2 strangulation
3 non malignant stenosis
4 other
118. Other complication(s) : 0 no
1 incisional hernia
2 complaints of bowel function (other than ileus)
3 other:
119. Date of re-operation (dd-mm-yyyy) :
120. Nature of re-operation :

**When completed, please fax this form to the coordinating center:
Dalhousie University, Halifax, Canada**

[contact]
